**STATEMENT OF COMPLIANCE**

This trial will be conducted in compliance with the protocol, International Council on Harmonization Good Clinical Practice (ICH GCP) and applicable state, local and federal regulatory requirements. Each engaged institution must have a current *Federal-Wide Assurance (FWA)* issued by the Office for Human Research Protections (OHRP) and must provide this protocol and the associated informed consent documents and recruitment materials for review and approval by an appropriate Institutional Review Board (IRB) or Ethics Committee (EC) registered with OHRP. Any amendments to the protocol or consent materials must also be approved before implementation.

The protocol, informed consent form(s), recruitment materials, and all participant materials will be submitted to the IRB for review and approval. Approval of both the protocol and the consent form(s) must be obtained before any participant is consented. Any amendment to the protocol will require review and approval by the IRB before the changes are implemented to the study. All changes to the consent forms will be IRB approved; a determination will be made regarding whether a new consent needs to be obtained from participants who provided consent, using a previously approved consent form by the IRB of record.

**1 PROTOCOL SUMMARY****1.1 SYNOPSIS**

Title:	Support Models for Addiction Related Treatment (SMART) Trial of Opioid Use Disorder in Pregnant Women
Grant Number:	MAT-2018C2-12891
Study Description:	
Between 1999 and 2014 the point prevalence of an Opioid Use Disorder (OUD) in pregnant women increased from 1.5 to 6.5 per 1000 deliveries, which is in line with rates of opioid prescribing in the general population.(1) Unfortunately, providers of outpatient medication assisted treatment (MAT) are less likely to treat pregnant women compared to non-pregnant women (75% vs 91%).(2) The provision of MAT in reproductive health settings may augment the capacity to treat pregnant women with an OUD and increase treatment rates, but the optimal models for care need to be determined. We propose a cluster randomized clinical trial to compare the effectiveness of two models of support for reproductive health clinicians to provide care for pregnant and postpartum women with an OUD: 1) a collaborative care (CC) approach based upon the Massachusetts Office-Based-Opioid Treatment (OBOT) Model,(3) that would provide onsite training, and support to providers and patients through the use of a care managers (CMs) vs 2) a telesupport approach modeled on the Project Extension for Community Healthcare Outcomes (ECHO), a remote education model that provides mentorship and guided practice and participation in a learning community, via video conferencing.(4)

Objectives:	
1) To determine differences in engagement and retention between participants who receive care from a center that uses a CC vs an ECHO support model. We hypothesize that the benefit from a CM and proactive monitoring approach will lead to greater treatment engagement and retention among patient participants.
 
<math>H_1</math>: Participants with an OUD are more likely to be engaged in care if the center is randomized to the CC vs the ECHO model of support.
 
<math>H_2</math>: Participants with an OUD treated in CC centers are more likely to be retained in MAT and/or non-pharmacological care for an OUD than those treated in a center randomized to the ECHO model of care.
 
2) To determine differences in patient-reported outcomes between the two treatment models. For this domain we will use the Patient Activation Measure (PAM) as the sentinel measure.
 
<math>H_3</math>: Participants in the CC, compared to the ECHO condition, will have higher PAM scores at week-36 and 3-months post-partum.

Endpoints:	Treatment Retention Treatment Engagement Patient Activation Measure (PAM) Birth Outcomes
Study Population:	264 pregnant women with opioid use disorder
Phase or Stage:	Phase 3
Description of Sites/Facilities:	12 characteristically matched obstetrical centers in Connecticut and Massachusetts.
Study Intervention/Experimental Manipulation:	Collaborative Opioid Prescribing Model (CC) Project ECHO (Extension for Community Healthcare Outcomes)
Study Duration:	4 years
Participant Duration:	Approximately 44 weeks (8 weeks pregnant– 3 months post-partum)

## 1.2 SCHEMA

## 1.3 SCHEDULE OF ACTIVITIES

	Study Screening	Visit 1  (Baseline)	Visit 2 	Visit 3 	Visit 4 	Visit 5  26 Week Visit	Visit 6 	Visit 7 	Visit 8  36 Week Visit	Visit 9 	Visit 10  Birth	Visit 11  3 Months post-partum visit
Window						+/- 4 weeks			+/- 4 weeks			+/- 4 weeks
Informed Consent	X											
NIDA Quickscreen	X											
Demographics	X											
Concomitant Medication		X	X	X	X	X	X	X	X	X		
Medical History		X								X		
Pregnancy Questionnaire	X											
Urine Drug Screening 			X-----						X-----X			
DSM-5 OUD Checklist 	X											
Contact Information						X						
Assigned OUD Treatment 			X-----						X-----X			
Time Line Follow Back 	X	X	X	X	X	X	X	X	X	X		
Post Traumatic Stress Disorder Checklist for DSM-5 (PCL-5)	X											
Fagerstrom Test for Nicotine Dependence (FTND)	X				X				X			X
HIV Risk-Taking Behavior Scale (HRBS)	X											
Patient Activation Measure (PAM)	X				X				X			X
Shared-Decision Making Questionnaire-9 (SDM-Q-9)	X				X				X			X
Perceived efficacy in Patient-Physician Interactions Questionnaire (PEPPI)	X				X				X			X
Kim Alliance Scale-Communication subscale (KAS-CM)	X				X				X			X
PROMIS Emotional Short Form 4a	X				X				X			X
PROMIS Satisfactions with Roles and Activities Short form 8a	X				X				X			X
Satisfaction with Roles and Activities	X				X				X			X
Edinburgh Postnatal Depression Scale (EPDS)	X				X				X			X
Adverse Childhood Experience Questionnaire	X											
Stigma Related Rejection Scale					X							X
Treatment Utilization Form	X	X	X	X	X	X	X	X	X	X		
Substance Abuse Attitude Survey (Treatment Optimism) 												

Physicians Worklife Survey(PWS) 									
Birth Outcomes) 									x
Qualitative Interviews (sub group)				x					x

1. Standard of care urine drug screens will be tested for the presents of illicit and licit opiate drugs at every prenatal visit after consent. Results are recorded by the clinic staff and faxed to the Yale research assistant.
2. Participants will receive OUD treatment via the clinic assigned treatment method (either CC or ECHO) throughout the length of their participation.
3. Participant will enter the study at different point of pregnancy. Therefore, it is likely that participants will complete varying numbers of visits between screening and the 26-week visit, and the 34-week visit and birth. This is expected and is not considered a protocol deviation. Visit 1 will follow immediately after the consenting process
4. The Time Line Follow Back will be conducted monthly during the length of the study. The number of TLFB assessments will vary depending on when the patient enters the study and when they give birth.
5. All participating centers will perform a drugs screen such as the NIDA Quick Screen or equivalent validated instrument as standard of care. If it is positive the DSM-5 OUD checklist will be completed to determine study eligibility.
6. The DSM-5 OUD Checklist will be administered to any patients who have a positive NIDA Quick Screen as part of the standard of care.
7. Birth outcomes include: low birth weight, resuscitation at delivery, fetal demise, preterm birth, duration of hospitalization.
8. The Substance Abuse Attitude Scale, the Physicians Worklife Survey and the Qualitative Interviews will be completed by physicians And done prior to the first participant being enrolled at the site and after the last participant is enrolled at the site.

## 2 INTRODUCTION

### 2.1 STUDY RATIONALE

In 2015, an estimated 3.8 million individuals in the US misused pain relievers and over 1.9 million suffered from an OUD.(5, 6) The lethality of opioid misuse is staggering in that more than 90 people in the US die each day from an opioid overdose for a total of 33,000 deaths in 2015.(7) Pregnant women have not been spared. About 5% of pregnant women report nonmedical use of opioids in the prior year and 1% report nonmedical use in the preceding month.(8) Similarly, an analysis of commercial insurance beneficiaries finds that 2.2% of pregnant women were dispensed opioids at least 3 times in pregnancy.(9) Not only is nonmedical use of opioids a problem in and of itself, it primes individuals to transition to illicit opioids such as heroin. National data from the Centers for Disease Control found a startling upsurge in the rates of an OUD among obstetrical inpatients, increasing 333% from 1.5 to 6.5 cases per 1000 deliveries between 1999-2014. (1) Although data from **Connecticut (CT)** were not available for this analysis, the rate of change in **Massachusetts (MA)** was 6th out of the 30 states and the District of Columbia that contributed data.

The potential consequences of maternal opioid misuse in pregnancy are documented extensively and include maternal and fetal effects. **Neonatal opioid withdrawal syndrome (NOWS)** has received widespread attention (10) as rates of maternal opioid use have risen. National estimates for NOWS show escalations from 3.4 to 5.8 per 1000 hospital births between 2009 and 2012. (11) In utero opioid exposure also increases the risk of premature rupture of membranes,(12) preterm birth,(12) small for gestational age delivery,(13) and still birth.(12) On the maternal side, opioid use in pregnancy is associated with placental abruption, preterm labor, cardiac arrest and death.(12) Indeed, a recent analysis finds that the 300 percent increase in opioid use among pregnant women during the study period paralleled an upsurge in cardiac events, the leading cause of death in pregnancy.(14) The annual

percent increment in risk of an acute heart attack or cardiac arrest between 2002 and 2014 was 13% for women who used opioids during pregnancy. (14) These data illustrate the need for treatment of an OUD in pregnancy.

The context for women who misuse opioids in pregnancy needs to be considered. For example, poverty, unstable housing, interpersonal violence and food insecurity occur frequently among women with an OUD; these factors can influence maternal, fetal and neonatal health.(15-18) General medical conditions can complicate pregnancy. About 60-70% of pregnant women who inject drugs and use opioids in pregnancy are positive for Hepatitis C (19, 20) and ~1% are HIV positive.(21) As well, co-use of substances that have deleterious effects on maternal and fetal outcomes,(22-26) particularly benzodiazepines, cocaine, nicotine and alcohol, are a problem.(27-29) A third component to morbidity derives from concurrent psychiatric illness confronting pregnant women with substance use disorders. Among women with non-medical prescription opioid use, more than 40% have a depressive or anxiety disorder.(30)

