## 9.2 SAMPLE SIZE DETERMINATION

We plan to recruit a sample of 6 matched pair clusters (total of 12 clusters), with 6 clusters per condition and 20 patients per cluster for a total of 264 patients. Hypothesizing that CC will perform better than ECHO, this sample size achieves 80% power to detect a clinically meaningful minimum difference of 0.20 between the CC proportion (0.94) and the ECHO proportion (0.74).

To estimate the sample size needed to test differences between models of care in the proportion of women retained in treatment at delivery using a permutation test, we used the method of Hayes and Bennett (1999) for matched-pair cluster randomized trials. Our null hypothesis is  $p_{ECHO} = p_{CC}$  and the alternate hypothesis is  $p_{ECHO} \neq p_{CC}$ , where  $p$  is the proportion of women retained in treatment at delivery, setting a two-sided type 1 error rate of 0.05. We based the estimate of the proportion in the CC on a study by our co-investigator in which 94% of patients treated under a CC model continued MAT until delivery.

We could not find empirical data for an estimate of the coefficient of variation, so we followed the approach of Hayes and Bennett (1999). We generated 10,000 data sets with 6 clusters each, with true proportions assumed uniformly distributed between 0.72 and 0.99 to allow for a relatively wide range of plausible retention proportion values. In each of the simulated data sets coefficient of variation values were calculated based on formula (9) in the manuscript. This follows the conservative approach

suggested on p.322 of the paper (i.e. to use the coefficient of variation between clusters within each group as an upper limit for the coefficient of variation in matched pairs designs). After examining the distribution of the resulting coefficient of variation we selected 0.10 as the value for our subsequent power calculations since more than 90% of the data sets had values under that threshold.

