In an ongoing study of mothers with depression randomized to cognitive behavioral therapy with or without a community ambassador, 37% of 103 participants increased by at least one PAM level. ([name], 2019, personal communication) Using this proportion for the CC group, 40 participants per site will provide 80% power to detect a 15% difference in the proportion of women who increase at least one PAM level between CC and ECHO. These estimates assume a two-sided test, with a significance level of 0.05 and an estimated within-pair coefficient of variation between clusters (CV) of 0.10.

For minimum detectable effect sizes for secondary outcomes at 80% power (assuming two-sided alpha = 0.05, 6 CC sites, 6 Echo sites, 40 participants per group, CV=0.1) we generated the table below.

Table 2 Continuous Outcomes	Mean (std. dev.) in Collaborative Care Group	Minimum detectable difference	Effect size (Cohen's d)
Birth weight	3137 (629)	597	0.95
Dichotomous Outcomes	Proportion for Collaborative Care Group	Minimum detectable difference	Effect size (Risk Ratio ECHO:CC)
Retained on MAT	0.89	0.20	0.78
PAM- increased 1 level*	0.37	0.20	0.46

We were not able to assess power for the remaining secondary outcomes: physician work-life survey and engagement with MAT given the limited prior research on these topics.

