#### 9.4.2 ANALYSIS OF THE PRIMARY ENDPOINT(S)

We updated our analysis plan on 1.30.24 since two sites recruited only one participant. We wanted to make use of the data from their matched pairs rather than having to drop 4 sites from our analyses. Thus, to increase the efficiency of our matched pair design and maximize data utilization from all sites we will not account for the matching of clusters in our analyses.

We will test differences between treatment groups in the proportion of participants who are engaged and retained in treatment using generalized linear mixed models (GLMM). GLMM models will include a random effect for site to account for potential positive correlations among observations within sites and will evaluate the fixed effect for the interventions. For the PAM outcome, we plan to conduct linear mixed models, where the response variable will be the PAM score at the week-36 assessment and at 3-months post-partum. Models will include a random effect for site and will evaluate fixed effects for the interventions and baseline PAM scores. If assumptions of normality are violated, we will consider transformations or alternative distributions to determine the model with the best fit. Due to the small number of samples, we will use small sample corrections in our mixed models. For continuous outcomes we will use Satterthwaite's degrees of freedom approximation given the small number of clusters and high variability in size of clusters in our study. For binary outcomes we will use restricted pseudo-likelihood with between-within correction to the degrees-of-freedom.

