#### 9.4.3 ANALYSIS OF THE SECONDARY ENDPOINT(S)

To tests differences in secondary patient outcomes between care models groups, we will use GLMM as described above.

Our co-Investigator, [name] will collect and analyze qualitative data. Qualitative interviews will be will be audio recorded, transcribed, and independently coded by two trained masters level researchers who will be supervised by [name]. All transcripts will be de-identified. The team will develop codes to be used in the content analysis(102, 103) and utilize these codes to identify themes related to deployment of the two models. Themes will be examined both within and across informant groups. The team will use NVivo (104) to analyze data. Subsequent to the initial training, two staff will independently code each transcript and meet together with [name] to compare codes, discuss and work towards consensus in order to build a common understanding and use of codes.(105) [name] will review interrater reliability on a regular basis in order to prevent coder drift and will retrain staff as needed. The collection of data from multiple informants, iterative process of data collection and analysis and use of two researchers to code transcripts, increases creditability, transferability, dependability, and confirmability of the findings.(105, 106)

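### The birth-weight model leaves out baseline nicotine dependence, which the trial collects and names as a fetal risk; pre-specifying it is a modest, nearly free gain

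*Combined protocol and SAP*

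**What the plan says.** Birth weight is a secondary outcome with a directional hypothesis favouring collaborative care (sections 3 and 9.1). For its analysis, section 9.4.3 states: "To tests differences in secondary patient outcomes between care models groups, we will use GLMM as described above". The model described above, in section 9.4.2, carries a random site effect and "will evaluate the fixed effect for the interventions". The only baseline covariate named there is the baseline PAM score, and it applies to the PAM outcome alone. The same section drops the pair matching from the analysis.

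On the exposure, section 2.1 warns that "co-use of substances that have deleterious effects on maternal and fetal outcomes,(22-26) particularly benzodiazepines, cocaine, nicotine and alcohol, are a problem". The FTND is marked at Study Screening in the Schedule of Activities (1.3), is listed in section 8.1.1, and is repeated at three later assessments. It appears in no hypothesis, in no row of the outcome table in section 3, and in no model.

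Two other sections come near the issue. Section 9.4.4 compares baseline characteristics by arm but does not say what follows from a difference. Section 9.4.6 allows individual-level covariates, concurrent substance use among them, in descriptive and exploratory analyses of effect heterogeneity.

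**The concern.** Twelve sites are randomised and the women are enrolled afterwards. Enrolment is by a designated staff person, who at collaborative-care sites is the care manager (section 5.5), so the enroller knows the arm. Sites were matched on state, size and academic status (section 6.3), not on substance use. With so few units the arms can differ in smoking at entry by chance, and differential recruitment could add to that.

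The trial collects a measure of the exposure but does not plan to use it in this comparison. If an imbalance appears in the baseline table, any adjustment made then would be a choice made after seeing the data. At stake are the position and width of the interval for one secondary outcome.

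**Working it through.** **Inputs from the plan.** Table 2 in section 9.2 gives birth weight 3137 g (SD 629 g) under collaborative care and a minimum detectable difference of 597 g (d = 0.95). The setting is "For minimum detectable effect sizes for secondary outcomes at 80% power", with the assumptions given as "assuming two-sided alpha = 0.05, 6 CC sites, 6 Echo sites, 40 participants per group, CV=0.1". For retention, section 9.2 says "we used the method of Hayes and Bennett (1999) for matched-pair cluster randomized trials"; I take Table 2 to rest on the same method.

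**Step 1: reproduce 597 g.** For c pairs, m women per site and coefficient of variation k:

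c = 2 + (1.960 + 0.842)² × [2·SD²/m + k²(μ₁² + μ₂²)] / d², with μ₂ = μ₁ − d.

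Put in c = 6, k = 0.10 and m = 40 per site. At d = 598.6 the within-site term is 2 × 629²/40 = 19,782. The between-site term is 0.01 × (3137² + 2538.4²) = 162,842. Then 2 + 7.849 × 182,624 / 598.6² = 6.0. So d = 598.6 g, within 0.3% of 597 g, and 597/629 = 0.95. Reading 40 as per arm gives 734 g, so Table 2 evidently means 40 per site.

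**Step 2: how much a person-level covariate can remove.** Within-site noise is 19,782/182,624 = 11% of the variance. The rest is between sites: a CV of 0.10 means a site SD of 0.10 × 3137 = 314 g, an ICC of 314²/(314² + 629²) = 0.20. Multiply the within-site term by (1 − R²) and, in the second variant, the between-site term as well. R² is not in the documents; I take 0.05 to 0.30.

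| Basis | R² = 0 | 0.05 | 0.10 | 0.20 | 0.30 |
|---|---|---|---|---|---|
| Plan's basis (matched, 40 per site), within-site only | 598.6 | 597.1 | 595.6 | 592.6 | 589.6 |
| Plan's basis, both levels | 598.6 | 584.6 | 570.2 | 539.8 | 507.3 |
| Unmatched, 20 per site, within-site only | 566.0 | 563.4 | 560.9 | 555.7 | 550.4 |
| Unmatched, 20 per site, both levels | 566.0 | 552.6 | 538.8 | 509.8 | 478.8 |

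The lower rows follow the current text: matching dropped, and "6 clusters per condition and 20 patients per cluster for a total of 264 patients" (264/12 is in fact 22 per site, which gives 561.3 g unadjusted). On the plan's basis the fall is 0.3 to 1.5% within sites only, and 2 to 15% at both levels. On the current basis the within-site fall is 0.5 to 2.8%. If the true CV were 0.02, R² = 0.20 would cut 271 g to 243–247 g, or 9 to 10%.

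**Step 3: size of a chance imbalance.** Assume prevalence p of 0.5 to 0.7, between-site SD s of 0.05 to 0.15, sites of 20, and an effect of 200 to 300 g. None of these assumed prevalences or effects is in the documents. The variance of the arm difference in prevalence is 2[s² + (p(1−p) − s²)/20]/6.

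- p = 0.7, s = 0.05: SD = √(0.012875/3) = 6.6 points; × 200 g = 13 g.
- p = 0.5, s = 0.15: SD = √(0.033875/3) = 10.6 points; × 300 g = 32 g.

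For scale, the unadjusted standard error on the plan's inputs with 20 per site and equal means is √{[2 × 629²/20 + 0.01 × 2 × 3137²]/6} = √39,397 ≈ 198 g. An imbalance SD of 32 g is then 32²/39,397 = 2.6% of the sampling variance.

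**Step 4: which baseline measures are safe.** The schedule and section 8.1.1 agree that FTND is taken at screening/baseline. They do not agree on the Timeline Follow-Back (TLFB). The schedule marks it at screening, but 8.1.1 omits it. Sections 4.1 and 8.1.3 describe a monthly contact by a research assistant, which 4.1 places after enrolment. Section 5.5 pays for an initial phone interview separately from screening and baseline.

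**The case against.** The strongest reply is that an unadjusted secondary analysis is legitimate and that the gain is close to nothing on the plan's own inputs. Chance differences between sites in smoking are part of the between-site variance, and the random site effect with its small-sample correction carries them into the standard error. Section 9.4.4 would show an imbalance, and section 9.4.6 already plans mixed models with individual covariates. All of this stands. It leaves a narrower gap: 9.4.6 is exploratory, is aimed at heterogeneity, does not name nicotine and defines no adjusted birth-weight estimate.

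The reply is also right about TLFB. If the first interview follows enrolment, adjusting for it could condition on something the intervention changes, since section 2.3.3 expects collaborative care to reduce co-use.

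Two stronger readings are tempting. A reader might infer that the unadjusted estimate is biased or its test invalid. Chance imbalance in a randomised comparison is imprecision and not bias, and the documents do not show that recruitment actually differed by arm. A reader might also multiply an imbalance of 16 to 21 points, reached in about one trial in 20 at an assumed 65% prevalence and site SD of 10 to 15 points, by an assumed 150 to 350 g and quote a shift of about 25 to 75 g. That is a tail event joined to undocumented effects, and it should not be presented as the expected size.

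**Conclusion.** The point holds as a modest improvement to one secondary outcome. The text is clear that the birth-weight model has arm and site only, while baseline FTND is available. The precision gain is small because the plan's CV of 0.10 makes between-site variation dominant. It would be larger if the covariate also explained site differences or if the true CV were smaller.

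The better reason to act is pre-specification. The random site effect does not correct a systematic difference in who is enrolled in each arm, and a baseline covariate can correct the part of it that is measured.

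The figures assume equal sites and normal quantiles, whereas section 9.4.2 reports two sites with one participant each. They also treat the exposure as a perfectly measured yes/no variable; a dependence score that captures it imperfectly will remove less.

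**What to change.** 1. In section 9.4.3, pre-specify baseline FTND as a participant-level fixed effect in the birth-weight model. Keep the random site effect and the Satterthwaite correction, and report the unadjusted estimate alongside. Use no later FTND value.
2. State when the first TLFB is done and what window it covers, reconciling the schedule with sections 4.1, 5.5, 8.1.1 and 8.1.3. Add cocaine, benzodiazepine and alcohol co-use to the model only if that window ends before enrolment.
3. In section 9.4.8, for exploratory scales collected at baseline (SDM-Q-9, PEPPI, KAS-CM, PROMIS, EPDS), use each scale's own baseline score as a covariate, as section 9.4.2 does for PAM. This follows from consistency; I have not estimated its gain.

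The cost is a few lines of text. FTND needs no new data collection, and a participant-level covariate uses no site-level degrees of freedom. The small downside is handling missing baseline values, for which a rule should be stated.
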